6.5.3 Burn Wound Closure

At each weekly visit, the Investigator will assess epithelialization (as a percentage of the burn wound). When the burn wound is fully re-epithelialized (i.e., 100%), without drainage and without need of a dressing, the burn wound will be considered "closed".

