7. STATISTICAL DESIGN

7.1 EVALUABILITY

All subjects who receive study medication will be evaluable for the safety analysis. All subjects who are randomized to receive study medication will be evaluable for the intent-to-treat analysis.

Unless specified otherwise, SPSS® Version 10.0 or higher will be utilized to perform the statistical analyses of efficacy and safety measures.

Categorical variables will be summarized in general using frequencies and percentages, whereas continuous variables will be summarized in general using descriptive statistics of number of observations (n), mean, standard deviation (SD), minimum (Min), median, and maximum (Max).

Hypothesis testing, unless otherwise indicated, will be performed at the 5% significance level. All P values will be rounded to four decimal places; P values less than 0.0001 will be presented as '<0.0001' in all tables. All group comparisons from analysis of variance (ANOVA) and/or analysis of covariance (ANCOVA) models will be based on Type III sums of squares. All confidence intervals will be two-sided with 95% coverage.

Missing or invalid data of efficacy assessments will be handled by individual scales or subscales on the basis of each individual assessment. Missing data for individual items will be assessed for each assessment of each scale and imputed with the mean score of the corresponding assessment and rounded up to the nearest integer if the number of items with missing data or invalid is less than or equal to 20% of total item number. Otherwise, the assessment score will be set to missing.

Considering that a subject's burn wound may be healed and/or a subject may discontinue from the study prior to the end of the study period, missing values at each weekly visit due to either burn wound healing or early termination or any other reasons will be imputed in this study prior to deriving the efficacy endpoints for evaluation, using the technique of last-observation carried forward (LOCF). By so doing, a burn wound that heals sooner will be given more weight for efficacy.

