7.1.1 Primary Efficacy

The primary objectives of the study include the proportion of subjects with the burn wound healed after 3 weeks of treatment, time (in weeks) to healing, and incidence of burn wound infection.,

Both the proportion of subjects with burn wound healed after 3 weeks of treatment and the time to heal between the two treatment groups will be analyzed using ANOVA. Also, the proportion of burn wounds healed at each of the 5 assessments (visit 2,3,4,5, and 6) between the two treatment groups will be analyzed through a mixed-effect ANOVA. The incidence of burn wound infection observed over the study will be compared between the two treatment groups, using a t-test.

The analysis of the primary efficacy evaluations will be performed for the ITT population.

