8. SAMPLE SIZE JUSTIFICATION

A previous study of Santyl vs. white petrolatum in normal volunteers with dermatome wounds enrolled 28 subjects, each of whom served as their own control (paired wounds, treated differently). At 9 months follow-up, the Santyl treated wounds had lower total scores on the Vancouver Scar Scale, suggesting the efficacy of Santyl ointment, although the difference between Santyl and its petrolatum vehicle was not significant (P = 0.09, Wilcoxon signed-rank test).

The current study uses a parallel-group design and non-uniform injuries on different individuals, which are more likely to lead to a larger variance as compared to the previous study. The injuries are non-uniform and different in nature compared to the dermatome study. Assuming a moderate effect size of 0.750 for the present study, the sample size of 80 (40 per group) will yield a statistical power of approximately 70% to detect a difference between the two treatment groups at the significance level of 0.05 (2-sided). Based on a two-sample t-test, the current study is comparable in power to the described previous study.

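### The yes/no primary endpoint of healing at 3 weeks is analysed by ANOVA: the test holds up, but the 95% interval can under-cover if one arm heals almost completely and the arms differ

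*Combined protocol and SAP*

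**What the plan says.** Section 7.1.1 deals with two of the three primary endpoints in one sentence: the proportion "healed after 3 weeks of treatment and the time to heal between the two treatment groups will be analyzed using ANOVA". The first of these is binary. Section 6.5.3 counts a wound as closed only "When the burn wound is fully re-epithelialized (i.e., 100%), without drainage and without need of a dressing", and Section 6.2.1 limits the analysis to one target wound per subject, so each subject is either healed or not.

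Section 7.1 sets the general rules: "Hypothesis testing, unless otherwise indicated, will be performed at the 5% significance level", and "All confidence intervals will be two-sided with 95% coverage". Section 7.1.1 names no interval for the healing difference. The interval follows from the general rule together with the named method; for a two-group ANOVA it is the pooled-variance t interval. No chi-square or exact test, logistic model or interval for proportions is named for any binary endpoint.

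Section 8 plans 40 per group from a standardised effect ("Assuming a moderate effect size of 0.750 for the present study"), and no Day 21 healing rate is stated or assumed anywhere.

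**The concern.** ANOVA treats a 0/1 outcome as if it were normal with equal variance in both arms. At moderate proportions and 40 per arm this is harmless. Near 100% it is not: an arm in which every wound has closed contributes no variance, so the interval is too short, and it collapses to a point if both arms are fully closed.

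High healing at 3 weeks cannot be ruled out. The synopsis limits the trial to partial thickness burns under 10% TBSA that need neither hospital admission nor a graft. Healing at 3 weeks is the first-named primary endpoint, and its estimated difference and interval are what readers will take from it. What is at stake is whether that interval has the coverage that Section 7.1 states.

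**Working it through.** **Inputs.** n = 40 per arm (Section 8; 1:1 allocation in Section 6.1); two-sided 95% intervals and a 5% test level (Section 7.1); a binary endpoint (Section 6.5.3). The true healing rates p1 and p2 are assumptions, shown as a range.

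**Formulas.** With x and y healed, a = x/40 and b = y/40:
- Pooled variance: s² = [40a(1−a) + 40b(1−b)]/78.
- ANOVA interval: (a − b) ± t × √(s² × 2/40), with t = 1.991 on 78 df.
- Coverage: the sum, over all 41 × 41 = 1,681 tables, of Bin(x; 40, p1) × Bin(y; 40, p2) for those tables whose interval contains p1 − p2.
- Newcombe interval, with (l, u) the Wilson limits in each arm: lower limit a − b − √[(a − l1)² + (u2 − b)²], upper limit a − b + √[(u1 − a)² + (b − l2)²].

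**Step 1: where the stated 95% is reproduced.** ANOVA coverage is 94.7% (85% v 95%), 94.4% (90% v 95%), 95.8% (90% v 96%), 94.4% (90% v 97%) and 95.7% (95% in both arms).

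**Step 2: near the ceiling, with unequal rates.**

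| True rates | ANOVA | Newcombe | Miettinen-Nurminen |
|---|---|---|---|
| 90% v 98% | 91.1% | 98.0% | 96.8% |
| 90% v 99% | 90.8% | 97.0% | 95.3% |
| 95% v 98% | 86.5% | 98.7% | 97.2% |
| 95% v 99% | 86.9% | 99.7% | 99.0% |

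Closer to 100% the ANOVA figure falls further: 80.1% for 96% v 99% and 75.2% for 97.5% v 99%. The edge is not sharp: 90% v 97% gives 94.4%, but 95% v 97% gives 91.2% and 94% v 97% gives 90.4%. A wide gap can also protect: 85% v 98% gives 93.2%.

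**Step 3: why it fails.** Take 95% v 98%, a true difference of −3 points. Whenever the 95% arm happens to close all 40 wounds, the interval misses −3 points. Against 40/40 it runs from 0 to 0, and against 39/40 from −2.5 to +7.5 points. The chance of 40/40 in that arm is 0.95^40 = 12.9%, which is nearly all of the 100 − 86.5 = 13.5% non-coverage.

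**Step 4: zero width.** If both arms truly heal at 98%, all 80 wounds close with probability 0.98^80 = 19.9%, and the ANOVA interval is then 0 to 0. For the same data the Wilson limits are 40/(40 + 3.84) = 0.912 to 1, so the Newcombe interval is ±√[(1 − 0.912)² + 0²], about ±8.8 points.

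**Step 5: the test.** For N = 80 in two groups, Pearson X² = 80R² and F = 78R²/(1 − R²). The F critical value is 1.991² = 3.963, so ANOVA rejects when R² > 3.963/(78 + 3.963) = 0.04836, that is, when X² > 3.869. The chi-square test rejects when X² > 3.841. No 40 v 40 table has X² between these values, so the two tests agree in all tables. With equal rates from 50% to 99%, type I error peaks at 5.9% (near 90-91%) and falls to 0.1% at 99%.

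**The case against.** The strongest reply is that the trigger is narrow and the documents do not point to it. At 97.5%, only one subject of 40 is unhealed. Section 5.2 admits deep partial thickness burns, Section 6.5.3 sets a strict definition of closure, Section 4.2 allows up to six weeks of treatment, and Section 2.1 says second degree burns can need several weeks. Under LOCF on the ITT set (Section 7.1), a subject who leaves with an open wound before Day 21 stays open; two such subjects hold an arm at 38/40 = 95%. All of this stands, and it limits the point to a conditional one. It does not remove it: no rate is given, and the method has to be fixed before the rate is known.

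It is also fair to say that Section 7.1.1 promises no interval for this endpoint. The promise comes only from the general sentence in Section 7.1.

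Three stronger readings are tempting but not supported:
- A reader might infer that high healing alone breaks the interval. It does not. With both arms between 80% and 95%, coverage stays at about 93-96%; with both arms at 98% it is 99.3%, because the zero-width interval then contains the true difference of zero.
- A reader might infer that ANOVA will declare differences that a proportions test would not. At 40 per arm it decides exactly as the Pearson test does, and in every table with at least one wound open and one closed it rejects exactly when the Miettinen-Nurminen interval excludes zero.
- A reader might infer coverage near 81% from uneven arms. That figure (95% v 98%) needs a 34/46 split with the lower rate in the smaller arm; with the arms reversed it is 90.3%. A split at least that uneven has a 22% chance under simple randomisation, but in both directions together, and Section 8 plans 40 per group.

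**Conclusion.** The point holds as a defect of the interval, not of the test. Using ANOVA for this endpoint does no material harm to the significance decision, or to the interval while both arms heal at up to about 95% (about 97% in some pairs). If one arm heals at about 97.5% or more and the other is moderately lower, coverage falls to about 86-91%; it is lower still if both rates are closer to 100%. If all wounds close, the interval carries no information about uncertainty.

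This rests on three assumptions: 40 analysed per arm, the pooled t interval as the one implied by ANOVA, and Day 21 healing rates that the documents do not supply. It concerns the single Day 21 comparison, not the mixed model over five visits or the t-test for infection. It is a modest point, worth correcting because the endpoint is primary and the correction is easy.

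**What to change.** In Section 7.1.1, separate healing at Day 21 from time to healing. For healing at Day 21, state that the difference in proportions between arms is reported with a 95% interval for proportions, Newcombe or Miettinen-Nurminen, and tested by Pearson chi-square at the two-sided 5% level. Name one interval in advance. Miettinen-Nurminen has the advantage that, at 40 per arm, it agrees with the Pearson decision in every table with at least one wound open and one closed. Newcombe differs from Pearson in 8 of the 1,681 tables, all sparse, but holds coverage of at least 94.3% for rates from 50% to 99%.

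The cost is one sentence and no new data. Intervals become somewhat wider near 100%: for 38/40 v 40/40 the ANOVA interval is −11.9 to +1.9 points and the Newcombe interval −16.5 to +4.5 points. Coverage then tends to exceed 95% (98.0% and 98.7% for Newcombe at 90% v 98% and 95% v 98%). At 40 per arm, power does not change, because the test decision does not change.

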4.2 USAGE

Santyl and bacitracin will be applied daily to the thickness of a nickel (2 mm) on the burn until the wound heals, with a maximum application period of six weeks.

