6.2.2 Visits 2 to 6 [weekly (±2 days) visits after 1st visit]

- 1. Query subject (or caregiver) regarding any changes in general health and the use of concomitant medications.
- 2. If any adverse events are observed or reported, they must be recorded as instructed in Section 9, *Adverse Events*.
- 3. Assess the burn wound. The assessments include exudate type and amount, odor, presence of eschar, presence of epithelial islands, peri-burn skin characteristics & rash, pain, and itching (refer to Section 13).
 - If it is decided that topical antibiotics will be initiated to treat a burn wound infection, the subject must be discontinued from the study. The use of systemic antibiotics does not require subject discontinuation.
- 4. Evaluate re-epithelialization of the burn wound. Complete the visit based on the status of the burn wound as outlined below.

If the burn wound is not completely re-epithelialized ("open"), complete the following steps:

1. A staff member should apply the test article and the dressings to the burn wound while demonstrating to the subject (or caregiver) the proper application of ointment and dressing(s).

Instruct the subject (or caregiver) that:

- a. Only the ointment and dressings prescribed should be applied to the burn wound during the study.
- b. Application of the study ointment and changing the dressings must occur each day.
- c. Test articles are not to be used on any other person or to treat any other burn wound.
- 2. Instruct subject (or caregiver) to refrain from using excluded medications, to treat the burn wound as instructed, and to return to the office for the next sequential visit.

If the burn wound is completely re-epithelialized ("closed"), complete the following steps:

- 1. Photograph the burn wound per standard of care.
- 2. Only moisturizer (Aveeno with Oatmeal) and compression dressing may be used on the scar until the next scheduled study visit. Moisturizer should be used two times per day and as needed. Compression should be used at all times (approximately 23 hours per day).
- 3. Instruct the subject (or caregiver) to continue avoiding any prohibited concomitant medications and to return for the next evaluation at day 90 (±2 weeks). Any scheduled study visits between the current visit and first scar assessment visit not be completed.
- 4. Instruct subject to return to clinic for follow up scar assessment visits 7-8.

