6.2.3 Scar Assessment visits 7 to 8 [90 (± 2 weeks), and 180 (±2 weeks), Days After Visit 1]

- Query subject (or caregiver) regarding any changes in general health and the use of concomitant medications.
- 2. If any adverse events are observed or reported, they must be recorded as instructed in Section 9, *Adverse Events*.
- 3. Per SOC photograph the scar at all visits or at any other visit if the subject is discontinuing.
- 4. Provide subject (or caregiver) with the Subject Scar Assessment Scale and ask them to complete an assessment without input from study personnel beyond simple instructions and explanations of terms (refer to Section 13).
- 5. Ask the subject to rate the pain and itch of the scar (refer to Section 13).
- 6. The Investigator or sub-investigator completes the Vancouver Scar Scale (refer to Section 13).

- 7. Once wound healing is confirmed, the subject (or caregiver) will use compression and moisturizer daily 4 weeks post wound healing. Moisturizer should be used two times per day and as needed. Compression should be at all times (approximately 23 hours per day).
 The subject (or caregiver) will use compression and moisturizer for 6 months after wound healing is confirmed only if instructed by the investigator.
- 8. At all visits, remind the subject (or caregiver) to avoid any prohibited concomitant medications and to return for the next evaluation per the protocol visit schedule.

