6.3 DISCONTINUED SUBJECTS

6.3.1 Definition and Procedures

Discontinued subjects are those who voluntarily discontinue participation, who are withdrawn for safety reasons, or who have missed 2 or more consecutive study visits or 3 or more consecutive test article doses so as to be ineligible for continued study participation. Subjects who discontinue the study prior to completing all of the regularly scheduled visits should complete the visit procedures for the visit at which the subject is being discontinued. If appropriate, the Investigator should also advise the subject of subsequent therapy and/or procedures necessary for their medical condition.

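### Time to healing, a primary endpoint, is to be analysed by ANOVA in all randomised subjects, but wounds never seen to close have no healing time and the plan assigns none

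*Combined protocol and SAP*

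**What the plan says.** Time to healing in weeks is one of three primary objectives (Sections 3 and 7.1.1). Section 7.1.1 says that "the time to heal between the two treatment groups will be analyzed using ANOVA" and that "The analysis of the primary efficacy evaluations will be performed for the ITT population". Section 7.1 defines ITT as everyone randomised.

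Closure is judged at five weekly visits. The heading of Section 6.2.2 is "Visits 2 to 6 [weekly (±2 days) visits after 1st visit", so Visit 6 falls at week 5. Section 4.2 allows ointment until healing, "with a maximum application period of six weeks", which is one week beyond Visit 6. Table 1 (Section 12) schedules the closure evaluation at Visits 1 to 6 and not at Visits 7 and 8. Section 7.1.3 nevertheless compares open or closed status at every study visit.

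Two routes out of the study before healing are foreseen. Under Section 6.2.2, if "topical antibiotics will be initiated to treat a burn wound infection, the subject must be discontinued from the study". Under Section 6.3.1, subjects are discontinued who "have missed 2 or more consecutive study visits or 3 or more consecutive test article doses".

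The only relevant missing-data rule is in Section 7.1: "missing values at each weekly visit due to either burn wound healing or early termination or any other reasons will be imputed" by last observation carried forward before the endpoints are derived. No survival method, censoring rule or assigned healing time appears anywhere in the document.

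**The concern.** ANOVA needs a number for every subject it includes. A wound open at Visit 6 has no healing week, and neither does a subject who left with an open wound. Carrying the last observation forward fills in the status open, which is enough for the proportion healed but does not yield a time.

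The analyst must then do one of two things that the plan does not mention:

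- **Drop these subjects.** This contradicts ITT and compares only the healed. Being healed by week 5 is itself a result of treatment, so the comparison loses power and can change sign.
- **Give them a ceiling value.** This keeps the direction, but the size of the difference and the power then depend on the value chosen.

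The trial is unblinded (synopsis), so either choice could be made with the results in view. Exits for infection make matters worse: infection is another primary outcome, and those exits are probably related to slow healing.

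**Working it through.** **The plan's own figure.** There is none for time to healing. Section 8 gives one power figure: about 70% for a standardised effect of 0.750, 40 per group, two-sided 5%, two-sample t-test. The normal approximation gives 0.75 × √(40/2) − 1.96 = 3.354 − 1.960 = 1.394, so power is about 91.8% (91.2% by the exact t). That mismatch is a separate point. The calculation follows a discussion of scar scores, and it assumes an outcome for all 80 subjects.

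**Timing.** Visit 6 is day 35 ± 2 (33 to 37). Visit 7 is day 90 ± 14 (76 to 104), counted from Visit 1 as in Section 6.2.3. The gap is 76 − 37 = 39 to 104 − 33 = 71 days. The six-week treatment maximum is day 42. A wound that closes after Visit 6 has no scheduled visit to date it.

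**Simulation inputs.** From the plan: 40 per arm, looks at weeks 1 to 5, two-sided 5%. Assumed: all healing rates, because the documents give none. There were 20,000 to 40,000 trials per scenario, so the simulation standard error is at most √(0.25/20,000) = 0.35 points.

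**Scenario A, healing rate doubled throughout.** If a share *q* of control wounds is open at week 5, the weekly control hazard is *h* = 1 − *q*^(1/5) and the treated hazard is 1 − (1 − *h*)².

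| Control open at week 5 | *h* control | *h* treated | Power, open wounds dropped | Power, 6-week ceiling | Power, log-rank |
|---|---|---|---|---|---|
| 5% | 0.451 | 0.698 | 69% | 82% | 83% |
| 10% | 0.369 | 0.602 | 57% | 82% | 83% |
| 20% | 0.275 | 0.475 | 37% | 80% | 82% |
| 33% | 0.199 | 0.358 | 22% | 76% | 78% |

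With constant hazards of 0.35 against 0.20 (12% against 33% open), power is 19% dropped, 66% with a 5-week ceiling, 70% with a 6-week ceiling and 73% by log-rank.

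**Scenario B, benefit only in slow wounds.** Half of wounds are slow. Their weekly hazards are 0, .05, .2, .35, .4 (treated) and 0, .02, .05, .1, .1 (control). Fast wounds are alike in both arms.

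One set can be worked by hand, with fast hazards .4, .5, .6, .6, .6:

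- Fast wounds: share healed 0.9808, sum of week × probability 1.972.
- Slow, treated: share healed 0.7036, sum 2.722.
- Slow, control: share healed 0.2459, sum 0.978.
- Mean week among the healed, treated: (1.972 + 2.722)/(0.9808 + 0.7036) = 2.79.
- Mean week among the healed, control: (1.972 + 0.978)/(0.9808 + 0.2459) = 2.40.
- Share open at week 5: treated 1 − (0.9808 + 0.7036)/2 = 15.8%; control 1 − (0.9808 + 0.2459)/2 = 38.7%.

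The treated arm heals far more wounds yet looks about 0.4 weeks slower once open wounds are dropped, because its late-healing slow wounds enter the average and the control arm's do not.

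With a ceiling *c*, the mean is half the sum of the two week × probability totals plus *c* times the share open. The difference, treated minus control, is (2.722 − 0.978)/2 − *c* × (0.387 − 0.158) = 0.872 − 0.229*c*. That is −0.27, −0.50 and −0.73 weeks for *c* = 5, 6 and 7. Simulated power is 12%, 22% and 30%.

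Across five sets of fast-wound hazards (38 to 44% of control wounds open):

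| Method | Significant, right direction | Significant, wrong direction |
|---|---|---|
| Open wounds dropped | under 0.5% | 13–20% |
| 5-week ceiling | 11–14% | under 0.5% |
| 6-week ceiling | 21–25% | under 0.5% |
| Log-rank | 42–44% | under 0.5% |

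With only 20% slow wounds (17% of control wounds open, same fast set as the hand calculation), the dropped analysis is wrong-direction significant in 8% of trials, against 2.5% nominal. Power is 8% with a 6-week ceiling and 11% by log-rank.

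**Null.** With equal healing and no difference in exits, every method rejects in about 5% of trials.

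**Unequal exits, equal healing.** Assume that 24% against 5% of slow wounds exit. Censoring at exit makes the arm with more exits look significantly better in 5.7% of trials. Counting exits as not healed makes the arm with fewer exits look significantly better in 4.8%. Nominal is 2.5% for each.

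**The case against.** The strongest reply is that the plan leans towards keeping everyone. The primary analysis is ITT, values are imputed after early termination, and Section 7.1 says that earlier healing will carry more weight. On that reading open wounds get a ceiling, and under proportional hazards a six-week ceiling costs only 1 to 2 points in Scenario A and 3 points in the constant-hazard case. Type I error is sound. The wrong-direction figures need both dropping and a large share of slow wounds, which nothing in the documents supports for minor outpatient burns. The week-3 proportion, also primary, needs no healing time.

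Much of this stands as a limit on size. The wrong-direction results are conditional as stated, and the effects are small at 20% slow wounds. It does not close the gap: no ceiling is given, and in Scenario B moving it from 5 to 7 weeks changes power from 12% to 30%.

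A second reply is that counting exits as not healed gives up the log-rank advantage. With 10% random exits, all kept as not healed, and the healing rate doubled, log-rank power is 67/70/73/71% for 5/10/20/33% open. The six-week ceiling gives 68/72/74/70%. Log-rank with exits censored gives 81/81/80/76%. This is a fair reason to limit the not-healed rule to infection exits and to report both versions.

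A closure date recalled at Visit 7 is also weaker than the Section 6.5.3 definition, which rests on the investigator's assessment.

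**Conclusion.** The concern holds and should be corrected before analysis. A primary endpoint is undefined for part of the population in which it is to be analysed, and ANOVA cannot use those subjects without a rule that the plan does not contain. This follows from the text and needs no assumed rate.

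The size does rest on assumptions. With a doubled healing rate and 20% of control wounds open at week 5, the plausible readings differ by 80 − 37 = 43 points of power. With a late benefit in half of wounds they differ in direction. If few wounds are open at week 5, or a six-week ceiling is fixed in advance and hazards are proportional, the loss is small. The fault is an unstated choice with possibly large consequences; not every form of ANOVA would fail.

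**What to change.** 1. Replace ANOVA for time to healing with Kaplan-Meier curves and a log-rank test, or a discrete-time or interval-censored hazard model suited to weekly looks, in all randomised subjects.
2. Censor wounds that are still open, and exits for reasons other than infection, at the last closure assessment.
3. Keep exits for topical treatment of infection as not healed through Visit 6 in the main analysis. Report censoring at exit as a sensitivity analysis, since neither rule is free of bias when exits differ between arms.
4. Reconcile the six-week maximum in Section 4.2 with the last weekly visit at week 5 in Section 6.2.2, and the closure row of Table 1 with Section 7.1.3.
5. For wounds open at Visit 6, record closure status at Visit 7 and any reported closure date. Status supports an interval-censored analysis; treat the recalled date as supportive only.

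Adjustment for baseline target-wound area and laser Doppler perfusion, both already collected at Visit 1, is optional. It would add precision and does not correct this problem.

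The cost is SAP wording, standard software procedures and one extra item on the Visit 7 form. No extra patients or visits are needed.

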6.2.4 Unscheduled Visits

Unscheduled exams may be conducted at the discretion of the Investigator with all obtained information recorded in the source documents and on the Unscheduled/Interim Visit pages within the CRF.

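### Time to healing, a primary endpoint, is analysed by ANOVA although wounds never seen to close have no healing time and the plan has no censoring rule

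*Combined protocol and SAP*

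**What the plan says.** Section 7.1.1 lists three primary variables: the proportion healed after 3 weeks, time to healing in weeks, and incidence of burn wound infection. For the second, "the time to heal between the two treatment groups will be analyzed using ANOVA". It adds: "The analysis of the primary efficacy evaluations will be performed for the ITT population". Section 7.1 defines that population as everyone randomized.

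Closure is observed at visits. Section 6.5.3: "At each weekly visit, the Investigator will assess epithelialization (as a percentage of the burn wound". Section 7.1.1 counts these looks when it refers to "the proportion of burn wounds healed at each of the 5 assessments (visit 2,3,4,5, and 6". Visits 2 to 6 are weekly after Visit 1, so Visit 6 is nominally Day 35. Section 4.2 allows treatment for up to six weeks, one week longer.

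Subjects can leave with an open wound. Under section 6.2.2, where "topical antibiotics will be initiated to treat a burn wound infection, the subject must be discontinued from the study". Under section 6.3.1, discontinued subjects include those "who have missed 2 or more consecutive study visits or 3 or more consecutive test article doses".

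The only missing-data rule that bears on this is in section 7.1: "missing values at each weekly visit due to either burn wound healing or early termination or any other reasons will be imputed", by last observation carried forward. No section names a survival method, a censoring time, or a value for a wound never seen to close.

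**The concern.** ANOVA on a time needs a completed time for each subject analysed. Two groups will not have one: subjects still open at Visit 6, and subjects discontinued while open. They are not a random subset. The first group holds the slowest healers, and the second includes infected wounds treated topically.

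The analyst would have to choose between dropping these subjects and assigning a number such as Week 5 or Week 6. The first contradicts the ITT statement, and nothing in the plan supports the second. The estimated difference and the power depend on the choice. In an open-label trial, that choice for a primary endpoint should be fixed before the data are seen.

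The Visit 6 gap does not affect the healed proportion at Day 21 or the infection comparison.

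**Working it through.** **Does any rule in the plan supply the missing time?**

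- *LOCF (7.1).* For an early leaver it carries open forward. That settles healed/not healed at each visit but gives no week of healing. For a subject open at Visit 6 no weekly value is missing, so LOCF does nothing.
- *Unscheduled visits (6.2.4).* "Unscheduled exams may be conducted at the discretion of the Investigator". They are optional and cannot be relied on.
- *Visits 7 and 8.* Section 6.5.5 implies closure once a Vancouver score is recorded, and section 7.1.3 compares open/closed status at each study visit. However, neither section 6.2.3 nor Table 1 has a closure assessment at these visits. Visit 6 falls on Days 33 to 37 and Visit 7 on Days 76 to 104, so a closure first seen at Visit 7 is known only to within 76 − 37 = 39 to 104 − 33 = 71 days.

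Nothing fills the gap.

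**How large could the effect be?**

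The plan gives no planning figure for time to healing, so there is none to reproduce. It also gives no open rate at Day 35 and no discontinuation rate. The inputs are 40 per arm and two-sided 0.05 (section 8), the weekly visits, and these assumptions:

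- healing time log-normal with log-SD 0.5, rounded up to the next weekly visit;
- Santyl median 20% shorter than bacitracin;
- bacitracin median 12.5 days (low case) or 23.0 days (high case), so Santyl 10.0 or 18.4 days.

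*Open at Day 35* = 1 − Φ(ln(35/median)/0.5):

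- Low: bacitracin 2.0%, Santyl 0.6%. Subjects open: 40 × (0.020 + 0.006) ≈ 1.
- High: bacitracin 20.0%, Santyl 9.9%. Subjects open: 40 × (0.200 + 0.099) ≈ 12.

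*Plausibility check.* Bacitracin healed by Day 21 = Φ(ln(21/median)/0.5) = 85% (low) or 43% (high). The high case is an upper scenario.

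*Early leavers.* Assume a 10% cumulative chance of leaving by Week 5 if still open, that is 1 − 0.9^(1/5) = 2.1% per week, with exit before that week's assessment. The expected number with no healing time, summed over arms, is 40 × [1 − Σ p(k) × 0.9^(k/5)] for k = 1 to 5, where p(k) is the probability of healing in week k. This gives about 5 or 16 of 80.

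*Mean difference, bacitracin minus Santyl, no early leavers.* Full follow-up uses Σ k p(k). Dropping uses Σ k p(k) / Σ p(k) over k ≤ 5. Week 6 coding uses Σ min(k, 6) p(k).

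| Rule | Low case (weeks) | High case (weeks) |
|---|---|---|
| Full follow-up | 0.41 | 0.74 |
| Drop open wounds | 0.36 | 0.35 |
| Code open wounds as Week 6 | 0.40 | 0.57 |

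*Power*, 4,000 simulated trials (Monte Carlo standard error about √(0.43 × 0.57/4000) = 0.8 points):

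| Analysis | No leavers, low / high | 10% leavers, low / high |
|---|---|---|
| ANOVA, drop | 40% / 27% | 39% / 25% |
| ANOVA, Week 6 | 43% / 46% | 32% / 39% |
| Weekly log-rank, censored | 43% / 44% | 43% / 41% |

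With equal medians and equal leaving, type I error is near 5% for all three.

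**Check under a different model.** Assume Weibull healing (shape 2), control median 3 weeks, healing hazard ratio 1.75 and 5% weekly dropout per arm (2,000 trials). Power is 25% (drop), 46% (code Week 5), 48% (code Week 6) and 59% (log-rank). With no true effect but unequal dropout, 3% against 10% per week, type I error is 6.5%, 7.7%, 10.6% and 5.6% in the same order.

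**The case against.** The strongest reply is that the defect is a missing rule, not the use of ANOVA. One sentence assigning Week 6 to wounds never seen to close would keep ANOVA and, with no early leavers, match log-rank on power (43% / 46% against 43% / 44%). That is correct for that setting. It does not hold once subjects leave while open: with 10% leavers, Week 6 coding falls to 32% / 39% against 43% / 41%.

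That gap depends partly on when leavers go. Section 6.3.1 asks discontinuing subjects to complete the visit at which they exit, which favours exit after the assessment. Then about 3 or 15 subjects lack a time, and power is 37% / 42% against 43% / 42%. The gap narrows in the low case and closes in the high case.

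Other points on that side:

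- These are minor burns under 10% TBSA that need no graft, so few may be open at Day 35. This stands, although deep partial-thickness burns are eligible.
- Shrinkage from 0.74 to 0.57 weeks under Week 6 coding is partly a change of quantity, to a mean restricted to six weeks. A rate ratio would not recover 0.74 weeks either. This stands.
- The inflated type I error needs unequal dropout, which is assumed. This stands.
- The synopsis and section 3 may already intend open/closed status at the scar visits. The wording is ambiguous, and section 6.2.3 and Table 1 provide no such assessment.
- The sample size rationale rests on a scar-scale study, so no planned power for time to healing is lost. This is true, but the endpoint is still primary.

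None of this supplies a healing time or a censoring rule.

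**Conclusion.** The concern holds. As written, the time-to-healing analysis cannot include every randomized subject unless every wound is seen to close by Visit 6, and the plan does not say what happens otherwise. That much follows from the text and needs no assumption.

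The size does rest on assumptions. The Visit 6 gap is negligible if about 2% of bacitracin wounds are open at Day 35. It is material at 20%, where dropping open wounds roughly halves the estimated difference (0.74 to 0.35 weeks) and costs about 17 points of power against a censored log-rank test (44% − 27%). Early leavers make the choice of rule matter even in the low case. Type I error is not a concern unless leaving differs between arms. The change should be made, with medium confidence in how much it will matter.

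**What to change.** In section 7.1.1, replace the ANOVA for time to healing with a discrete-time (weekly) or interval-censored survival analysis, and censor subjects not seen to close at their last closure assessment. Add an investigator-assessed open/closed field, using the section 6.5.3 definition, to section 6.2.3 and Table 1 at Visits 7 and 8. Treat a wound open at Visit 6 and closed at Visit 7 as interval-censored between those visits. As a sensitivity analysis, count subjects discontinued for infection as not healed through Visit 6.

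The cost is one case report form field at two existing visits and a change of method, with no extra visit, subject or treatment restriction. There are three drawbacks. Late healers have intervals of 39 to 71 days. The result is a healing-rate ratio, not a difference in mean weeks. Censoring at discontinuation assumes that leaving is unrelated to healing, which is doubtful for infection exits and is the reason for the sensitivity analysis.
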